10.3.1. Laboratory Normal Reference Ranges

Quantitative laboratory measurements will be compared with the relevant laboratory reference ranges in SI units and categorized as:

- Markedly abnormal low (Panic low values)
- Low: Less than LLN and greater than Panic low
- Normal: result within the laboratory normal reference range (LLN and ULN limit included)
- High: greater than ULN and lower than Panic high values
- Markedly abnormal high (Panic high values)

Laboratory measurement panic values are included in [Appendix 3](#) and [Appendix 4](#).

10.4. Vital Signs

The following vital signs measurements will be reported for this study.

- Systolic blood pressure (SBP), (millimeter of mercury [mmHg])
- Diastolic blood pressure (DBP) (mmHg)
- Pulse (beats per minutes [bpm])
- Respiratory rate (breaths/min)
- Temperature (°C)
- Weight (kg)
- Height (cm)
- BMI (kg/m²) [derived as weight (in kg) / [height (in m)]²]

These vital signs (with the exception of the BMI which will be calculated programmatically) will be measured during the Screening Visit and each in-clinic scheduled visit. Height (cm) will be obtained at Screening Visit only.

The following summaries will be provided for vital signs data by treatment group and pooled JZP150 treatment groups by scheduled visit:

- Observed and change from baseline by visit
- Incidence of markedly abnormal criteria (as defined below) by visit

10.4.1. Vital Signs Markedly Abnormal Criteria

Markedly abnormal quantitative vital signs measurements will be identified in accordance with the following predefined markedly abnormal criteria as specified in [Table 8](#).

Jazz Pharmaceuticals
 {Statistical Analysis Plan - Protocol #}JZP150-201-02

Table 8: Vital Signs Predefined Markedly Abnormal Criteria

Variable (unit)	Low	High
SBP (mmHg)	≤ 90 mmHg AND change from baseline ≤ -20 mmHg	≥ 180 mmHg AND change from baseline ≥ 20 mmHg
DBP (mmHg)	≤ 50 mmHg AND change from baseline ≤ -15 mmHg	≥ 110 mmHg AND change from baseline ≥ 15 mmHg
Pulse (bpm)	≤ 50 bpm AND change from baseline ≤ -15 bpm	≥ 120 bpm AND change from baseline ≥ 15 bpm
Weight (kg)	percentage change from baseline $\leq -10.0\%$	percentage change from baseline $\geq 10.0\%$
Temperature (°C)	≤ 35.0 °C	≥ 39.0 °C

Note: bpm: Beats per minute. DBP: Diastolic Blood Pressure. kg: kilogram. mmHg: Millimeter of mercury. SBP: Systolic Blood Pressure

10.5. ECG

A standard 12-Lead ECG will be recorded with the participant resting supine for at least 5 minutes. Results from the central ECG core lab will be included in the reporting of this study. Triplicate ECGs will be measured at each specified visit, with repeat measures no more than 30 minutes apart. Average values of available measures will be calculated for each visit. The following ECG parameters will be reported:

- PR Interval (msec)
- RR Interval (msec)
- QRS Duration (msec)
- QT Interval (msec)
- QT Bazett's correction (QTcB) Interval (msec) [derived]
- QT Fridericia's correction (QTcF) Interval (msec) [derived]
- Mean HR (bpm)
- Sinus Node Rhythms and Arrhythmias
 - Normal Sinus Rhythm
 - Sinus Arrhythmia
 - Sinus Tachycardia
 - Sinus Bradycardia
- ECG Interpretation:
 - Normal
 - Abnormal

The following summaries will be provided for ECG data by treatment group and pooled JZP150 treatment groups by scheduled visit:

Jazz Pharmaceuticals
 {Statistical Analysis Plan - Protocol #}JZP150-201-02

- Observed and change from baseline by visit (for quantitative measurements)
- ECG parameters results will be listed over time.

10.5.1. ECG Specific Derivations

$$QTcF(msec) = \frac{QT (ms)}{\sqrt[3]{RR(ms)/1000}}$$

$$QTcB (msec) = \frac{QT (ms)}{\sqrt{RR(ms)/1000}}$$

10.5.2. ECG Abnormal Criteria

Abnormal quantitative ECG measurements will be identified in accordance with the following predefined markedly abnormal criteria ([FDA 2005](#)).

Observed values for QT interval, QTcB interval and QTcF will be classified as follows at each time point:

- > 450 msec (M) or 470 msec (F)
- > 480 msec
- > 500 msec

Change from baseline for QT interval, QTcB interval and QTcF will be classified as follows:

- >30 msec increase from baseline
- >60 msec increase from baseline

A listing of participants meeting markedly abnormal criteria as well as a listing of participants with abnormal ECG overall assessment will also be provided based on the Safety Analysis Set.

10.6. Other Safety Endpoints

10.6.1. Physical Examination

A full PE will include, at a minimum, assessments of the cardiovascular, respiratory, gastrointestinal (including liver), neurological systems, [REDACTED] [REDACTED]. Newly observed clinically significant abnormalities or worsening of pre-existing findings after screening will be captured as an AE in the Adverse Event eCRF. [REDACTED]

[REDACTED]

[REDACTED]

[REDACTED] Any abnormalities identified at the screening PE should be recorded as medical history.

Jazz Pharmaceuticals {Statistical Analysis Plan - Protocol #}JZP150-201-02

For a specific body system, participants with both baseline and a post-baseline value will be included for shift summaries. For computing percentages, the denominator will be the number of participants with a baseline and a post-baseline value for the specific body system.

10.6.2. Pregnancy testing

Participants with confirmed positive test results of pregnancy based on urine sample (confirmed by serum sample) will be listed.

10.6.3. Columbia-Suicide Severity Rating Scale

The C-SSRS is a widely used measure of suicidal ideation and behavior. The instrument reliably predicts a potential suicide attempt in those who had previously attempted suicide and is able to determine clinically meaningful points at which a person may be at risk for an impending suicide attempt (Posner et al 2011).

The following summaries will be provided for the C-SSRS data by scheduled visit and by treatment group and pooled JZP150 treatment groups:

- Number and percentage of participants with any suicidal ideation (i.e., having responded yes to any of the 5 types of suicide ideation) as well as broken down by type of suicidal ideation
- Number and percentage of participants with any suicidal behavior ((i.e., having responded yes to any of the 4 or 5 types of suicidal behavior, as applicable) as well as broken down by type of suicidal behavior
- Number and percentage of participants with any suicidal behavior or any suicidal ideation; a participant having reported both suicidal behavior and suicidal ideation will be counted only once
- Number and percentage of participants with self-injurious behavior without suicidal intent.

Missing data will not be imputed. C-SSRS parameters will be summarized by scheduled visit. All C-SSRS parameters will be presented in the participant data listing.

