8.3.6. Suicidal Ideation and Behavior Risk Monitoring

Participants being treated with JZP150 should be monitored appropriately and observed closely for suicidal ideation and behavior or any other unusual changes in behavior, especially at the beginning and end of the course of intervention. Participants who experience signs of suicidal ideation or behavior should undergo a risk assessment. All factors contributing to suicidal ideation or behavior should be evaluated, and consideration should be given to discontinuation of the study intervention.

When informed consent has been given, families and caregivers of participants being treated with JZP150 should be alerted about the need to monitor participants for the emergence of unusual changes in behavior, as well as the emergence of suicidal ideation and behavior and to report such symptoms immediately to the study investigator.

Baseline assessment of suicidal ideation and behavior/ intervention emergent suicidal ideation and behavior will be monitored during JZP150-201 using the C-SSRS. At the Screening Visit, the Baseline/Screening Version of the C-SSRS will be administered to participants to exclude any individuals with active suicidal ideation or behavior.

The Since Last Visit Version of the C-SSRS will be administered to participants at every clinic visit after their Screening visit, including the Baseline and Follow-up visits, as well as during telephone calls conducted between clinic visits. At the Screening Visit, any participant who reports active suicidal ideation (eg, a positive response to Question 4 or 5 on the C-SSRS) or behavior (eg, a positive response to any suicidal behavior question on the C-SSRS) will be excluded. At post-baseline visits, active suicidal ideation or behavior must be recorded as an AE and reported to the sponsor or designee within 24 hours of first knowledge of the event by study personnel. Please refer to [Appendix 4](#) for details on reporting other reportable experiences (OREs).

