9.4.5. Safety Analyses

All safety analyses will be made on the Safety Population. All safety analyses will be descriptive; no formal statistical testing will be performed and are further described in the SAP.

Adverse Event Analyses:

Adverse events will be mapped to system organ classes (SOC) and preferred terms using the Medical Dictionary for Regulatory Activities (MedDRA). The participant incidence of AEs, AEs related to study intervention, SAEs, AEs leading to discontinuation, and fatal AEs will be summarized. This overall summary will also provide AEs by maximum severity.

The participant incidence of AEs, AEs related to study intervention, AEs, and AEs leading to discontinuation will also be presented by SOC and preferred term (PT). Preferred term summaries may also be provided.

The participant incidence of an AE will be summarized; if a participant has multiple events with the same PT occurring in different periods, the event will be reported for each of those periods. If an AE continues from one period to the next without increase in severity, the event will be reported only for the period of the AE onset. Changes in the severity of an AE within a period will only be counted as one AE with the worst severity.

Vital Signs:

For each vital sign parameter, summary statistics will be provided for observed and change from baseline values by scheduled visit.

Physical Examinations:

Observed and change from baseline values for weight will be summarized descriptively by scheduled visit.

12-lead ECG:

Observed and change from baseline values for ECG intervals will be summarized descriptively. The number and percent of participants with values or change from baseline values in QT/QTcF exceeding certain thresholds will be tabulated.

Clinical Laboratory Evaluations:

Observed and change from baseline laboratory evaluations will be summarized descriptively.

C-SSRS:

Columbia Suicide Severity Ratio Scale parameters will be summarized by scheduled visit.

Marijuana Withdrawal Checklist

Marijuana Withdrawal Checklist parameters will be summarized by scheduled visit.

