7.2. Baseline and Study Day Definitions

7.2.1. Baseline

For the study assessments that are either clinician-reported or patient-reported outcomes (CAPS-5, CGI-S, CGI-C, PGI-S, PCL-5, B-IPF, ReQoL-10, SDS, PSQI, PSQI-A, ISI, PHQ-9, SIGH-A, MWC, and C-SSRS), the baseline value is defined as the initial value obtained on the date of the Baseline Visit (Day -1). If this value is missing, the last non-missing value obtained prior to the first dose of study intervention will be used as the baseline value. Repeat assessments performed on the same Baseline Visit date will be included in the clinical database as unscheduled assessment but will not be utilized for analyses. If the scheduled Baseline Visit occurred on the same day (Day 1) of first dosing, the assessment of the above-mentioned endpoints should be considered prior to first dosing.

For all other assessments, the last non-missing value obtained prior to the initiation of study intervention will be used as the baseline value.

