7.2.3. Analysis Windows

All scheduled, unscheduled, and early termination assessments will be summarized by derived analysis visit per [Table 3](#), regardless of if the visit was performed on-site or remotely. Visit dates will be mapped based on the scheduled period of each visit, with adjusted analysis-defined windows as specified in [Table 3](#).

Height, serum pregnancy, demographics, medical/surgical history, MINI, C-SSRS (screening/baseline version), and Life Event Checklist for DSM-5 (LEC-5) are only assessed at Screening Visit. The analysis window for these assessments is Day -40 up to -2.

CGI-S, PGI-S, CGI-C, PCL-5, and C-SSRS since last visit will be assessed at efficacy and safety follow-up visits. CAPS-5 will be assessed at efficacy follow-up visits (if applicable) but will not be assessed at the safety follow-up visit. PSQI-A, PSQI, ISI, MWC, and PHQ-9 will be assessed at safety follow-up visit but not at efficacy follow-up visits. AEs and prior/concomitant medications are monitored throughout the study.

Jazz Pharmaceuticals
{Statistical Analysis Plan - Protocol #}JZP150-201-02

A clinic visit at the end of Week 8 is also included for safety assessments, secondary efficacy assessments, sparse PK sampling and study intervention dispensation.

If multiple measurements are recorded within a single analysis window, including unscheduled or repeated assessments, early discontinuation assessments, as well as efficacy and safety follow-up assessments, the following rules will be applied to determine the observation from which assessment will be used for that analysis defined visit.

- If there are two or more observations within the same analysis window, then the non-missing observation closest to the scheduled Visit Day will be used in the analysis.
- If two observations are equidistant from the scheduled Visit Day, the on-treatment observation will prioritize over the off-treatment observation, with the exception for safety follow-up visit. If they are both on-treatment observations, then the non-missing observation with the latest collection date will be used in the analysis.
- If two observations are collected on the same day and this day is the closest to the scheduled Visit Day, for efficacy endpoints, the non-missing observation with the earliest collection time will be used in the analysis; for safety endpoints, the non-missing observation with the latest collection time will be included in the analysis.

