Data collected from safety follow-up visit between 7 to 28 days after the last dose can be mapped to the safety follow-up analysis visit. Safety follow-up visits that take place at > 28 days post last dose will be considered out of window and the data collected will not be used.

If an analysis window does not contain any observations, then the data will remain missing for the analysis visit.

Listings will include scheduled, unscheduled, repeated, retest, early termination, efficacy follow-up and safety follow-up data per nominal visits.

Jazz Pharmaceuticals
 {Statistical Analysis Plan - Protocol #}JZP150-201-02

Table 3: Analysis Windows for Assessments or Measurements

Study Period	Scheduled Visit (V)/ Week(W)	Scheduled Visit Day	CAPS-5, SDS ^a	CGI-S, PGI-S, PSQI, PSQI-A ^b , ISI ^b	PCL-5	C-SSRS	CGI-C	MINI, LEC-5, Height, Serum Pregnancy Test	B-IPF ^c , ReQoL-10 ^c , MWC	PHQ-9	SIGH-A ^d , PE	Laboratory, Vital Signs, ECG ^e , Breath Alcohol Test ^e , Urine Drug Screen ^e	Urine Pregnancy Test	Blood Sample PK ^f , AEA, PG ^g
Screening	V1	-40 up to -2	na	na	-40 up to -2	-40 up to -2	na	-40 up to -2	na	-40 up to -2	-40 up to -2	-40 up to -2	-40 up to -2	na
Baseline ^h / Randomization	V2	-1	-1	-1	-1	-1	na	na	-1	-1	-1	-1	-1	-1
Double-Blind Intervention	V3/W1	7±2	na	1-14	1-14	1-7	na	na	1-14	na	1-14	na	1-42	
	V4/W2 (call)	14±2	na	na	na	8-14	na	na	na	na	na	na	na	
	V5/W4	28±2	1-56	15-42	15-42	15-28	1-56	na	na	15-56	1-42	15-42	na	na
	V6/W6 (call)	42±2	na	na	na	29-42	na	na	na	na	na	na	na	na
	V7/W8	56±2	na	43-70	43-70	43-56	na	na	na	na	43-70	43-70	na	43-70
	V8/W10 (call)	70±2	na	na	na	57-70	na	na	na	na	na	na	na	na
	V9/W12	84 (-5, +2)	57-112	71-112	71-112	71-112	57-112	na	1-112	57-112	71-112	71-112	1-112	71-112
Efficacy Follow-up	V11a/W4	28	1-56	1-56	1-56	1-56	1-56	na	na	na	na	na	na	na
	V11/W12	84	57-112	57-112	57-112	57-112	57-112	na	na	na	na	na	na	Na
Safety Follow-up	Safety Follow-up	98(+5)	na	8-112	8-112	8-112	8-112	na	8-112	8-112	na	8-112	8-112	8-112

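### C-SSRS tables are by visit only: the windows can drop late forms that are within tolerance, and no table counts new or worsened ideation per participant

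*SAP*

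**What the plan says.** Protocol 8.3.6 gives the C-SSRS its purpose: "intervention emergent suicidal ideation and behavior will be monitored during JZP150-201 using the C-SSRS". The since-last-visit version is given at every clinic visit after Screening and at the Week 2, 6 and 10 calls.

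For reporting, protocol 9.4.5 says "Columbia Suicide Severity Ratio Scale parameters will be summarized by scheduled visit". SAP 10.6.3 repeats this ("The following summaries will be provided for the C-SSRS data by scheduled visit") and names four summaries: ideation, behavior, either one, and self-injury without suicidal intent. It adds a listing. SAP 8.3 adds a summary of the screening form.

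SAP 7.2.3 determines which form fills each row. "All scheduled, unscheduled, and early termination assessments will be summarized by derived analysis visit per" Table 3, and where a window holds more than one form, "the non-missing observation closest to the scheduled Visit Day will be used in the analysis". In Table 3 the C-SSRS windows are Days 1-7, 8-14, 15-28, 29-42, 43-56 and 57-70 for Weeks 1, 2, 4, 6, 8 and 10, and 71-112 for Week 12. The same table allows each of the first six visits two days either side of Days 7, 14, 28, 42, 56 and 70.

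There is also an adverse event route. Protocol 8.3.6 requires that after baseline "active suicidal ideation or behavior must be recorded as an AE". SAP 10.2 counts each participant once per preferred term and system organ class, by arm and for pooled JZP150.

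**The concern.** There are two linked problems.

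**Windows.** A form completed one or two days late is within tolerance but falls in the next visit's window. It then competes with that visit's own form and loses, because the rule looks at distance from the target day and not at content. Each form asks only about the time since the previous one, so the form that is kept does not repeat what the dropped form recorded. Unscheduled forms face the same rule, and these may be the ones prompted by a clinical change.

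**Missing count.** By-visit rows cannot be added up to an incidence: the same person may appear in several rows, or a different person in each. No planned C-SSRS table compares a participant's post-dose result with the pre-dose level. Laboratory tests, vital signs, ECG, physical examination and the marijuana withdrawal checklist all have a change-from-baseline or shift summary in the SAP. The C-SSRS has none.

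At stake is whether the report can state, by arm, how many participants had ideation begin or worsen after dosing. Protocol exclusion 5 bars recent item 4 or 5 ideation but admits people with items 1 to 3, so worsening from a non-zero level is possible.

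**Working it through.** The plan states no figure to reproduce. The check applies the Table 3 windows and the closest-day rule to visit days that the plan allows.

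**Example 1, late scheduled form.** Week 1 takes place on Day 9 (allowed range 5-9) and Week 2 on Day 14. Both fall in Days 8-14. Distances from Day 14 are 5 and 0, so the Day 14 form is kept. The Week 1 row is empty, and the recall for Days 1-9 is in no row.

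**Example 2, unscheduled form.** An unscheduled form on Day 21 and the Week 4 form on Day 28 both fall in Days 15-28. Distances are 7 and 0, so the Day 21 form is dropped. The Day 28 form asks only about the time since Day 21.

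**How often scheduled forms are lost.** A completer has 8 scheduled post-dose forms (Weeks 1, 2, 4, 6, 8, 10, 12 and safety follow-up). Six can be displaced. Week 12 (Days 79-86) always stays in its own window.

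Let q be the chance that a visit is 1-2 days late, independent across visits and with full attendance. The documents give no value, so q is an assumption.

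- A late form at Weeks 1 to 8 is lost if the next visit is in its own window: probability q(1−q) for each of five visits. If the next visit is also late, the form is tabulated one visit too far along.
- A late Week 10 form (Day 71-72) is always lost to Week 12: probability q.
- Expected forms lost = 5q(1−q) + q.
- Any late visit leads to at least one lost form, so P(at least one) = 1 − (1−q)^6.

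| q (assumed) | Forms lost of 8 | Share of forms | Completers losing at least one form, whatever its result |
|---|---|---|---|
| 0.05 | 0.2375 + 0.05 = 0.29 | 3.6% | 26% |
| 0.10 | 0.45 + 0.10 = 0.55 | 6.9% | 47% |
| 0.20 | 0.80 + 0.20 = 1.00 | 12.5% | 74% |
| 0.40 | 1.20 + 0.40 = 1.60 | 20% | 95% |

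The last line corresponds to visits spread evenly over the five allowed days. Enumerating all 5^6 = 15,625 combinations, with Week 12 on Day 84, gives 14,896 with a loss (95.3%) and a mean of 1.6 forms lost, in agreement with the formulas.

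**What the adverse event tables recover.** Behavior and active ideation must be recorded as adverse events, so they have a per-participant count by preferred term. Protocol 8.3.6 illustrates active ideation with Questions 4 and 5, as examples and not as a cutoff. Item 1 to 3 ideation may also enter, because Appendix 4 counts exacerbation of an existing condition as an adverse event and makes suicidal ideation an expedited report with no item threshold. For those items, entry to the tables depends on an adverse event judgment. The SAP text shows no table of the expedited reports, and its special-interest categories in 10.2.1 are neurological, so no grouped suicidality row is specified.

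**The case against.** The strongest reply is that this is a reporting preference. Safety analyses are descriptive, protocol and SAP agree with each other, and protocol 8.3.6 commits to monitoring and not to an incidence table. Much of that stands, and it limits the point in four ways.

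- A reader might infer that suicidal behavior after dosing is counted nowhere. The documents do not support that: the mandatory adverse event recording and the once-per-participant rule in SAP 10.2 give a count by preferred term. What is missing is one grouped C-SSRS count.
- A reader might infer that data disappear. They do not. SAP 7.2.3 lists scheduled and unscheduled data by nominal visit, and 10.6.3 lists all C-SSRS parameters.
- A reader might take the last column of the table as the share of suicidal signals missed. It counts people who lose any form, most of which could be negative. The share-of-forms column is the relevant one. It carries over to positive forms only if positives are no more common among late forms, and the 20% end assumes a spread of visit days that no document supports.
- A reader might infer a lapse in participant protection. Protocol 8.3.6 requires reporting within 24 hours, and the blinded committee in protocol 10.1.5 meets monthly with suicidal ideation and behavior on its list.

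The objection does not remove the window fault. Visits conducted as planned can be left out of the tables by a stated rule. Nor does a count by preferred term compare a participant with the pre-dose level.

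**Conclusion.** The point holds as a limited one about safety reporting by arm. The window fault follows directly from Table 3 and SAP 7.2.3 and needs no assumption. Its size does: from 3.6% to 20% of a completer's scheduled post-dose forms for assumed lateness of 5% to 40%, with independent visits and full attendance. Loss of unscheduled forms is additional and cannot be sized.

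The missing baseline-linked, any-time count mainly affects new or worsened item 1 to 3 ideation, together with the lack of a single behavior count. How much item 1 to 3 ideation would escape the adverse event tables cannot be determined from the documents. No efficacy result or error rate is affected. The change is worth making because it is cheap, not because a conclusion depends on it.

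**What to change.** 1. **SAP Table 3 and 7.2.3.** Extend the C-SSRS windows to cover the two-day tolerance, for example Days 1-9, 10-16, 17-30, 31-44, 45-58 and 59-72, with Week 12 from Day 73. Each then contains its visit's full allowed range (5-9, 12-16, 26-30, 40-44, 54-58, 68-72, 79-86). Where several C-SSRS forms share a window, use the worst value instead of the closest.

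2. **SAP 10.6.3.** Keep the by-visit rows and add one descriptive table by treatment group and pooled JZP150, on the Safety Analysis Set, using all post-dose forms including unscheduled ones:
   - number and percent whose maximum post-dose ideation category exceeds their pre-dose maximum;
   - number and percent with any post-dose suicidal behavior;
   - a shift table of pre-dose against maximum post-dose ideation category.

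   For the first and third items, take as denominator participants with a pre-dose and at least one post-dose form, the rule that SAP 10.6.1 uses for physical examination shifts.

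   Take the pre-dose maximum over the recent-period part of the Screening form and the Day -1 form. The SAP 7.2.1 baseline alone is too narrow: the Day -1 form covers only the time since Screening, so ideation present at Screening, absent by Day -1 and later recurring would be counted as emergent. The SAP should name the Screening recall period used.

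   Add a footnote that recall periods differ and that the post-dose maximum spans more forms, so the table is for comparison between arms.

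The cost is one extra table and a small programming change. There is no new assessment and no test.
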